5.5 Study Treatment

All eligible subjects will be treated with ibrutinib PO and MEDI4736 IV in 28-day cycles. Prior to the first cycle, ibrutinib will be given daily for 7 days in the ibrutinib lead-in period prior to starting MEDI4736. On infusion days where pharmacokinetic, pharmacodynamic, or biomarker samples are drawn post-dose, MEDI4736 IV should be given first, with administration of ibrutinib as soon as possible after the end of infusion.

Missed doses of ibrutinib and MEDI4736 will not be made up. Dose modification of MEDI4736 will not be permitted.

Dosing of ibrutinib will continue up to 3 years as long as the subject is deriving clinical benefit (CR, PR, or SD) and the subject is not experiencing unacceptable toxicity. Dosing of MEDI4736 will continue for a total of 12 cycles of therapy if clinical benefit is seen without safety concerns. Toxicity may result in discontinuation or hold of one study drug while the other may continue to be dosed. Depending on the suspected relatedness to either agent (or both), the Investigator may perform dose modification and/or dose delays as per Section 5.6.1.4 and/or Section 5.6.2.5 at his or her clinical discretion. Re-treatment with MEDI4736 will not be allowed following completion of 12 cycles of treatment, regardless of any dose delays, missed doses, or following permanent discontinuation for any reason.

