10.7.1 Adverse Events

AE parameters to be evaluated are the type, incidence, and intensity of AEs; the relationship of AEs to study treatment; and the action taken with respect to study treatment due to AEs.

The verbatim terms used in the CRF by Investigators to identify adverse events will be coded using the Medical Dictionary for Regulatory Activities (MedDRA). Treatment-emergent adverse events (TEAEs) are those AEs occurring after the first dose of study treatment and within 30 days following the last dose of ibrutinib or within 90 days following the last dose of MEDI4736 (whichever date is later) OR will be collected until the start date of a new anticancer therapy that falls within this AE collection period; any AE that is considered study drug-related regardless of the start date of the event; or any AE that is present at baseline but worsens in severity or frequency after the first administration of study treatment or an AE that is subsequently considered drug-related by the Investigator. All TEAEs will be included in the analysis. For each AE, the number and percentage of subjects who experience at least one occurrence of the given event will be summarized. The number and percent of subjects with TEAEs will be summarized according to intensity (NCI CTCAE, Version 4.03) and drug relationship, as well as categorized by system organ class and preferred term. Summaries, listings, datasets, or subject narratives may be provided, as appropriate, for those subjects who die, who discontinue treatment due to an AE, or who experience a severe or a serious AE.

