1.1. Study Design

This is a Phase 1b/2, open-label multi-center study to assess the safety and efficacy of ibrutinib in combination with MEDI4736 in subjects with relapsed or refractory lymphomas. A 6+3 de-escalation design will be employed in Phase 1b to assess doses of ibrutinib in combination with MEDI4736 to determine the recommended Phase 2 dose (RP2D) for this study.

Phase 1b:

In the safety portion of the study, a starting dose of 560 mg of ibrutinib and 10 mg/kg of MEDI4736 will be explored in Cohort 1 and will follow a 6+3 dose de-escalation design including a sentinel subject with at least a 3-day observation period in each Phase 1b dosing cohort prior to dosing additional subjects to monitor for any unexpected acute or overlapping toxicities.

Subjects with one of the following two tumor types will be eligible for enrollment in Phase 1b:

- Follicular lymphoma (FL) (grade 1, 2, or 3A)
- Diffuse large B cell lymphoma (DLBCL)

In cohort 1, ibrutinib will be administered orally (PO) daily in 6 subjects at a dose of 560 mg in combination with MEDI4736 at a dose of 10 mg/kg intravenously (IV) every 2 weeks in 28-day cycles for 12 months or until unacceptable toxicity or disease progression occurs.

As a lead-in to the first cycle, ibrutinib will be given for 7 days prior to starting MEDI4736 in order to obtain single agent PK and biomarker samples that will be compared to combination therapy. Per the protocol, the 7-day lead-in period of ibrutinib is not part of the dose-limiting toxicity (DLT) evaluation period. The DLT assessment will occur from Day 1 of Cycle 1 of the combination therapy until the laboratory evaluations on Day 1 of Cycle 2 (28 days). If the subject incidence of DLTs from Day 1 of Cycle 1 of combination therapy to the laboratory evaluations on Day 1 of Cycle 2 is <33.3% (ie, ≤ 1 of 6 or ≤ 2 of 9 subjects with a DLT), this dose level will be considered safe to proceed to Phase 2, and will be defined as the RP2D. If 2 subjects within the initial cohort of 6 subjects experience a DLT, an additional 3 subjects will be enrolled at the same dose level. If 3 or more of 6-9 subjects experience a DLT, dose de-escalation will occur. A similar 6+3 cohort design will be utilized in the de-escalation cohorts. De-escalation cohorts -1A and -1B will be opened simultaneously to determine which dosing schedule is most appropriate for the Phase 2 portion of the study (for cohort definitions, see

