1.2. Endpoints

Primary Endpoints

Phase 1b:

- Recommended Phase 2 Dose (RP2D) of ibrutinib in combination with MEDI4736
- Safety and tolerability of ibrutinib in combination with MEDI4736

Phase 2:

- Overall Response Rate (ORR)

Secondary Endpoints

Phase 1b:

- Overall response rate (ORR)
- Duration of response (DOR)

Phase 2:

- DOR
- Progression-free survival (PFS)
- Overall survival (OS)

Safety Assessments

Safety and tolerability assessments include adverse events, clinical laboratory tests, and vital signs.

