2.1. Analysis Sets

Response-evaluable Population

The Response-evaluable Population is defined as all enrolled subjects who received at least one dose of study treatment (ibrutinib or MEDI4736) and provided at least one post-baseline response assessment. This population includes all the qualified subjects from both Phase 1b and Phase 2. The Response-evaluable Population will be used as the primary population for analyses based on overall response rate. In the analysis, subjects who had clinical progression per investigator will be included in the response-evaluable population.

Safety Population (Treated Population)

Safety population (Treated Population) includes all subjects who were enrolled in the study and received at least 1 dose of study treatment (ibrutinib or MEDI4736). The safety population will

be used to summarize the safety (including dosing) data and for the analysis of PFS, OS and ORR sensitivity analysis.

DLT Evaluable Population for Phase 1b

DLT evaluable population includes Phase 1b subjects who received study treatment and did not meet the criteria for subject replacement during the DLT observation period.

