4.2. Safety Analyses

Safety data will be summarized by tumor type cohorts. Table 2 summarizes the safety analyses to be performed for all tumor type cohorts.

Adverse events (AEs) will be coded in accordance with the Medical Dictionary for Regulatory Activities (MedDRA). Severity of AEs will be graded by the investigator according the NCI-CTCAE v4.03.

All laboratory values will be converted to and reported as international standard (SI) units. In general, only data from the central laboratory will be summarized and analyzed. Laboratory parameters will be graded using the NCI CTCAE v4.03.

Unless otherwise specified, only baseline and post-baseline values collected during the treatment-emergent period will be included in the safety analysis. A treatment-emergent adverse event is defined as any event that begins or worsens in either intensity or frequency on or after the first dose of study treatment (either ibrutinib or MEDI4736). Only treatment-emergent adverse events (TEAEs) occurring and reported during the study period will be included in the adverse event summaries. The TEAEs will be derived as those events that 1) occur after the first dose of study drug (either ibrutinib or MEDI4736), through the 30 days following the last dose of ibrutinib or 90 days following the last dose of MEDI4736 (whichever date is later); 2) any event with missing onset date and its resolution date during the treatment phase; 3) any event that is considered study drug-related regardless of the start date of the event; or 4) any event that is present at baseline but worsens in severity, seriousness, or becomes subsequently considered drug-related by the investigator.

Table 2: Summary of Safety Analyses

Safety Assessment	Definition	Analysis Methods
Safety and tolerability	
AE: TEAEs, SAEs, grade 3 or worse TEAEs, related TEAEs, TEAEs leading to treatment discontinuation, TEAEs leading to dose reduction, TEAEs leading to death, protocol- defined events of special interest, and other safety observations
 
Worst post-baseline toxicity grade for selected lab tests: Worst post-baseline toxicity grade, Hgb, creatinine clearance, abnormal uric acid, liver function abnormalities
 
Vital signs (blood pressure, heart rate, temperature, respiratory rate), and weight
	Descriptive summary statistics and/or listings

AE: adverse event; SAE: serious adverse event; TEAE: treatment-emergent adverse event

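### The planned safety tables pool the ibrutinib lead-in, the combination period and later ibrutinib alone, so they describe the whole regimen but do not isolate the safety of the combination

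*SAP*

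**What the plan says.** Among the Phase 1b primary endpoints, SAP 1.2 lists "Safety and tolerability of ibrutinib in combination with MEDI4736"; the other is the RP2D.

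SAP 4.2 defines one window for treatment-emergent events: those that "occur after the first dose of study drug (either ibrutinib or MEDI4736), through the 30 days following the last dose of ibrutinib", or through 90 days after the last MEDI4736 dose, whichever is later. Protocol 10.7.1 has the same start and the same later-of end ("AEs occurring after the first dose of study treatment and within 30 days following the last dose of ibrutinib", or the 90-day MEDI4736 limit). It also refers to the start of new anticancer therapy as an end to collection.

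The first dose is always ibrutinib, because "ibrutinib will be given for 7 days prior to starting MEDI4736" (SAP 1.1). The two drugs also stop at different times by design. Under protocol 5.5, "Dosing of MEDI4736 will continue for a total of 12 cycles of therapy", whereas "Dosing of ibrutinib will continue up to 3 years as long as the subject is deriving clinical benefit". The same section allows one drug to be held or stopped while the other continues.

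The safety population in SAP 2.1 is everyone who "received at least 1 dose of study treatment (ibrutinib or MEDI4736"; either drug is enough. Protocol 10.1.2 says the same. SAP section 2 sets baseline at or before the first dose of study treatment, that is, before ibrutinib. SAP 4.2 summarizes safety by tumor type cohort. Neither its text nor its Table 2 plans a split by treatment period or exposure-adjusted rates.

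**The concern.** The endpoint concerns two drugs given together, but the tables add up three planned exposures: ibrutinib alone for a week, both drugs for up to 12 cycles, then ibrutinib alone for as long as it continues. An event in lead-in week 1, before any MEDI4736, sits in the same row as one during Cycle 4 and one in the second year of ibrutinib alone.

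This matters because the known risks overlap and there is no control arm. Protocol 1.3.3.1 reports diarrhea in 35.9% of subjects on ibrutinib monotherapy, and 1.3.4.7 describes rash as common with ibrutinib. Protocol 1.4.3 lists enterocolitis and dermatitis among the potential immune-mediated risks of MEDI4736. Protocol 1.3.5 states that there are no clinical data on the combination in FL or DLBCL. A reader of the pooled table cannot tell whether diarrhea or rash began before, during or after combined exposure. The relatedness rows do not resolve this, because Table 2 does not split relatedness by drug.

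**Working it through.** The plan states no figure on this point, so there is none to reproduce. The check sets the TEAE rule against the dosing schedule, with the first lead-in dose as day 1.

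Inputs:
- Lead-in: 7 days (SAP 1.1).
- MEDI4736: Days 1 and 15 of 28-day cycles, at most 12 cycles (protocol Table 2 and 5.5). Check: 2 × 12 = 24 doses, the maximum given in protocol 1.6.3.
- Ibrutinib: up to 3 years (protocol 5.5).
- Window end: the later of last ibrutinib + 30 days and last MEDI4736 + 90 days (SAP 4.2).
- Assumed: ibrutinib for 18, 24 or 36 months (548, 730 or 1096 days). The documents give no distribution of treatment duration.

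**Full MEDI4736 course, then ibrutinib alone**

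- Last MEDI4736 dose (Cycle 12 Day 15): 7 + 11 × 28 + 15 = day 330.
- End of its 90-day tail: 330 + 90 = day 420.
- MEDI4736-exposed period, days 8 to 420: 413 days.
- Window lengths: 548 + 30 = 578, 730 + 30 = 760 and 1096 + 30 = 1126 days.
- Share outside = 1 − 413/window: 1 − 413/578 = 29%; 1 − 413/760 = 46%; 1 − 413/1126 = 63%.
- If only the 12 × 28 = 336 combination days count: 1 − 336/578 = 42%; 1 − 336/760 = 56%; 1 − 336/1126 = 70%.

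**Both drugs stopped together**

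- After Cycle 1: last MEDI4736 day 7 + 15 = 22, limit 22 + 90 = 112; last ibrutinib day 35, limit 35 + 30 = 65. The window ends on day 112. The lead-in is 7/112 = 6% of it, or 7/35 = 20% of dosing days.
- After Cycle 12: limits are 330 + 90 = 420 and 343 + 30 = 373. The window ends on day 420. The lead-in is 7/420 = 1.7% of it, or 7/343 = 2% of dosing days.
- The 90-day limit governs in both cases, so there is no ibrutinib-alone tail. One arises only when last ibrutinib + 30 exceeds last MEDI4736 + 90, that is, when ibrutinib runs more than 90 − 30 = 60 days beyond the last infusion.

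**Denominator**

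Assume 0 to 10% of subjects leave during the lead-in (the documents give no figure). A 20% rate of immune-related events among MEDI4736-treated subjects would then appear as 20% down to 0.90 × 20% = 18%. With counts, 7/35 = 20% becomes 7/39 = 18%: the same seven subjects.

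**The case against.** The strongest reply is that the pooled table is correct for what it describes. The lead-in and ibrutinib after Cycle 12 are planned parts of the regimen, and every combination-period event is in the table. A reader might infer that the tables fail to show the safety of the combination at all. The documents do not support that: the events are shown, but not separated. Nor is the pooling an invention of the SAP, since the window and population come from protocol 10.7.1 and 10.1.2.

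A reader might also infer that dose selection is compromised. It is not. SAP 1.1 counts DLTs from Cycle 1 Day 1 to the Cycle 2 Day 1 laboratory evaluations and expressly leaves out the lead-in. SAP 2.1 defines a separate DLT-evaluable set, and a Dose Level Review Committee reviews each cohort. That protects the RP2D, but it covers 28 days and cannot describe safety over up to 12 cycles.

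The size can be challenged too, and this challenge largely stands. The percentages are shares of calendar time for assumed long-stay subjects, not of subjects or events. Protocol 10.7.1 counts each subject once per event, so a later repeat adds nothing to incidence. SAP section 5 reports a substantial number of discontinuations for progression after one post-baseline assessment; those subjects contribute little or no tail.

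Finally, no window isolates combined dosing perfectly. One drug may stop while the other continues, protocol 8.3.1 foresees MEDI4736 alone, and after Cycle 12 the 90-day tail is itself ibrutinib-alone dosing. This bears on how the added column is labelled, not on whether to add it.

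**Conclusion.** The planned summaries cannot give a combination-period rate for any adverse event, although combination safety is one of the two Phase 1b primary endpoints. This is a gap in presentation that should be closed. It does not invalidate the main safety table, and the documents do not support replacing that table or moving it off the protocol's safety population.

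The effect depends on how many subjects continue ibrutinib well beyond MEDI4736, which the documents do not say. For a subject who completes MEDI4736 and takes ibrutinib for 18, 24 or 36 months, 29%, 46% or 63% of window time falls outside the MEDI4736-exposed period. For subjects who stop both drugs together, only the lead-in falls outside it. Denominator dilution is minor: about 2 percentage points on a 20% rate, even if 10% leave during the lead-in. No distortion of a specific event rate can be derived from these time shares.

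**What to change.** Keep the all-TEAE table on the safety population as the main table. Add to SAP 4.2 and Table 2 a by-period TEAE summary with three columns:

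- (a) Lead-in: first ibrutinib dose to the first MEDI4736 infusion (or to the end of the window if there is no infusion); all treated subjects.
- (b) MEDI4736-exposed period: first infusion to 90 days after the last; subjects with at least one infusion; events that start or worsen relative to status before dosing on Cycle 1 Day 1.
- (c) Ibrutinib alone thereafter, to the end of the TEAE window; subjects still at risk.

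Show person-time or exposure-adjusted rates for each column, because the periods differ greatly in length. Label column (b) as MEDI4736-exposed rather than combination, and say in a footnote that one drug may have been stopped while the other continued. Drug-related events that start after the window closes stay in the main table.

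No new data are needed. Event start and end dates are recorded (protocol 11.4.1), as are dosing interruptions and changes (protocol 5.6.1.4 and the end of 5.6.2.5). The Cycle 1 Day 1 pre-dose assessments (protocol 8.2.4) already include examination, vital signs, ECG, hematology, chemistry and TSH. The change is SAP wording and programming; the downside is a slightly longer table package.

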7.1.1.5. Adverse Events

The accepted regulatory definition for an AE is provided in Section 11.1. All medical occurrences that meet the AE definition must be recorded from the time the ICF is signed until 30 days after the last dose of ibrutinib and until 90 days after the last dose of MEDI4736 or until initiation of alternative cancer therapy. AEs will be recorded in the eCRFs from the administration of the first dose of the study drug and will continue to be recorded until 30 days after the last dose of ibrutinib and until 90 days after the last dose of MEDI4736 or until initiation of alternative cancer therapy. Laboratory abnormalities designated clinically significant by the Investigator will also be recorded as AEs. A clinical laboratory abnormality should be documented as an adverse event if any one of the following conditions is met:

- is associated with clinical signs or symptoms
- leads to additional treatment or to further diagnostic tests
- the abnormality is of a degree that requires active management; eg, change of dose, discontinuation of the drug, more frequent follow-up assessments, further diagnostic investigation, etc.
- results in study withdrawal
- is associated with a serious adverse event
- is considered by the Investigator to be of clinical significance

Additional important requirements for AE and SAE reporting are explained in Section 11.4.

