8.3.2 End-of-Treatment Visit for MEDI4736

An End-of-Treatment visit should occur 90 days (±7 days) after the last dose of MEDI4736 or prior to the start of a new anticancer treatment. This visit may occur as a standard Day 1 cycle study visit if the subject continues treatment with ibrutinib alone. Subjects who withdraw consent to treatment may still participate in the End-of-Treatment visit. The following procedures will be performed:

- Complete physical exam
- ECOG Performance Status
- Vital signs and weight
- Clinical laboratory tests for:
 - Hematology
 - o Serum chemistry
 - o TSH
 - o Urinalysis
 - Review of AEs and concomitant medications
- Research laboratory blood samples:
 - MEDI4736 pharmacokinetics

• MEDI4736 pharmacodynamics (includes anti-drug antibodies)

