11.4.2 Adverse Event Reporting Period

All AEs, whether serious or non-serious, will be documented in the source documents from the time the signed and dated ICF is obtained until 30 days following the last dose of ibrutinib and 90 days following the last dose of MEDI4736. SAEs will be reported to the Sponsor from the time of ICF signing. Non-serious AEs will be recorded in the eCRF from the first dose of study drug until 30 days after the last dose of ibrutinib and 90 days following the last dose of MEDI4736. If both study drugs were discontinued at the same time, an SAE after 30 days and up to 90 days from the last dose of study drugs should indicate the causality for MEDI4736 only and N/A for ibrutinib (unless there is a causal relationship to ibrutinib).

SAEs reported after 30 days following the last dose of ibrutinib and 90 days following the last dose of MEDI4736 should also be reported if considered related to study drug. Resolution information after 30 days following the last dose of ibrutinib and 90 days following the last dose of MEDI4736 should be provided.

Subjects who discontinued investigational product for unacceptable AEs will be followed until there is a return to the subject's baseline condition, or until the Investigator considers that a clinically satisfactory resolution is achieved. Subjects will also be contacted to document any new onset AEs and follow any AEs that were ongoing at the time of investigational product discontinuation.

Progressive disease should NOT be reported as an event term, but instead symptoms/clinical signs of disease progression may be reported (see Section 11.1.1).

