All AEs, regardless of seriousness, severity, or presumed relationship to study drug, must be recorded using medical terminology in the source document. All records will need to capture the details of the duration and the severity of each episode, the action taken with respect to the study drug, the Investigator's evaluation of its relationship to the study drug, and the event outcome. Whenever possible, diagnoses should be given when signs and symptoms are due to a common etiology (eg, cough, runny nose, sneezing, sore throat, and head congestion should be reported as "upper respiratory infection"). Investigators must record in the CRF their opinion concerning the relationship of the adverse event to study therapy. All measures required for adverse event management must be recorded in the source document and reported according to Sponsor instructions.

All deaths should be reported with the primary cause of death as the AE term, as death is typically the outcome of the event, not the event itself. Autopsy and postmortem reports must be forwarded to the Sponsor, or designee, as outlined above, if allowed per local regulatory guidelines.

If a death occurs within 30 days after the last dose of ibrutinib or 90 days after the last dose of MEDI4736, the death must be reported to the Sponsor as an SAE.

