5. MODIFICATION OF ANALYSIS TO THE PROTOCOL

Below is the major change made to the analyses in the protocol:

- The timing of interim analysis for the FL cohort is changed from “An interim analysis will be performed after 19 subjects are evaluable for tumor response after completing at least 2 response assessments” to “An interim analysis will be performed after 19 subjects are evaluable for tumor response after completing at least 1 response assessment” due to the number of early treatment discontinuations prior to 2 response assessments.
- The timing of the interim analysis for the DLBCL cohort is changed from “An interim analysis will be performed after 9 subjects are evaluable for tumor response after completing at least 2 response assessments.” to “An interim analysis will be performed after 9 subjects are evaluable for tumor response after completing at least 1 response assessment.
- Because of the substantial number of subjects who discontinued treatment due to PD after one post-baseline tumor assessment, the sponsors (Pharmacyclics and AstraZeneca) decided to hold the enrolment during the interim analysis.
- The terminology ‘Safety Assessments’ instead of ‘Safety Endpoints’ is used in Section 1.2 safety analysis part.

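### SAP 4.2 omits the protocol's limit on treatment-emergent events at the start of new anticancer therapy, so events recorded on the next line could enter the all-causality safety tables

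*SAP*

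**What the plan says.** SAP 4.2 derives treatment-emergent adverse events under four items. Item 1 takes events after the first dose of either drug "through the 30 days following the last dose of ibrutinib or 90 days following the last dose of MEDI4736 (whichever date is later". Item 3 adds any event considered related to study drug, whenever it starts. New anticancer therapy is not mentioned.

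Protocol 10.7.1 has the same window, "within 30 days following the last dose of ibrutinib or within 90 days following the last dose of MEDI4736 (whichever date is later", and continues: "OR will be collected until the start date of a new anticancer therapy that falls within this AE collection period".

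On what is recorded, the protocol gives two answers:

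- Section 7.1.1.5 runs recording "until 90 days after the last dose of MEDI4736 or until initiation of alternative cancer therapy".
- Section 11.4.2 has no such stop: "Non-serious AEs will be recorded in the eCRF from the first dose of study drug until 30 days after the last dose of ibrutinib", and likewise to 90 days after MEDI4736. Its death rule, which begins "If a death occurs within 30 days after the last dose of ibrutinib or 90 days after the last dose of MEDI4736", requires a serious adverse event report with no exception for subjects on another treatment. The adverse event row of Appendix 1 also runs to 30 and 90 days without a stop.

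SAP 5, which lists departures from the protocol, covers interim timing, the enrolment hold and a change of safety terminology. It does not mention the treatment-emergent window.

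**The concern.** Safety and tolerability is a primary objective in Phase 1b and a secondary objective in Phase 2, and there is no control arm. If an event that starts on the next line of treatment falls inside the SAP window and is in the database, the all-causality tables will show it as an event of the combination. No comparator rate is available to reveal the excess.

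The subjects most open to this are those who stop early. SAP 5 gives as its reason for the enrolment hold: "Because of the substantial number of subjects who discontinued treatment due to PD after one post-baseline tumor assessment". These subjects stop while MEDI4736 is still being given, so the 90-day tail applies to them almost in full, and relapsed lymphoma that has progressed is a common reason to change treatment.

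Because the protocol sections differ, two sites could record the same clinical course differently. Part of any reported rate would then reflect which section a site followed.

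**Working it through.** The plan states no figure to reproduce. The check has two parts.

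**1. The texts side by side**

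| Place | Runs to | Stops at new therapy? |
|---|---|---|
| Protocol 10.7.1 (analysis definition) | later of 30 / 90 days | Yes, worded as collection |
| Protocol 7.1.1.5 (recording) | 30 / 90 days | Yes |
| Protocol 11.4.2 (recording, deaths) | 30 / 90 days | No |
| Protocol Appendix 1 (adverse event row) | 30 / 90 days | No |
| SAP 4.2 item 1 (analysis definition) | later of 30 / 90 days | No |

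SAP 4.2 summarises only events that occurred and were reported during the study. That does not exclude an event recorded under 11.4.2 after new therapy began. Serious events and deaths are the likeliest to be there, since 11.4.2 requires them to be reported to the sponsor. They feed the serious, Grade 3 or worse and fatal summaries in SAP Table 2.

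**2. Length of the exposed period**

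Let *g* be the days from the last MEDI4736 dose to the last ibrutinib dose (*g* ≥ 0), and *s* the days from the last study dose to the start of new therapy. The documents do not give *s*, so the values below are assumptions.

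- Tail of the window past the last study dose: max(30, 90 − *g*).
- Days counted after new therapy starts: max(0, max(30, 90 − *g*) − *s*).

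| *g* | Tail (days) | *s* = 14 | *s* = 28 | *s* = 60 |
|---|---|---|---|---|
| 0 | 90 | 76 | 62 | 30 |
| 14 | 90 − 14 = 76 | 62 | 48 | 16 |
| 60 or more | 30 | 16 | 2 | 0 |

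The rows correspond to recognisable subjects. The first post-baseline assessment is at Cycle 3 Day 1 (protocol 3.1.2), during dosing every 2 weeks, and confirmed progression stops both drugs. With no missed MEDI4736 dose, *g* is then at most about 14, so the first two rows apply. The last row describes subjects who have been on ibrutinib alone for some time, as after 12 cycles.

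If item 1 ended at new therapy, every entry in the table would be 0. Events judged related to study drug would still be counted through item 3.

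**The case against.** The strongest reply is that such events will mostly not be collected. Two protocol sections, 7.1.1.5 and 10.7.1, stop collection at new therapy, and the visits fit that: the MEDI4736 End-of-Treatment visit falls "90 days (±7 days) after the last dose of MEDI4736 or prior to the start of a new anticancer treatment", the ibrutinib visit (8.3.1) is set up the same way, and survival follow-up (8.3.4) lists no adverse event review. If nothing is recorded, a SAP that counts what was recorded gives nearly the same result without repeating the limit. The 10.7.1 clause is also awkward. It is joined by an OR, worded as a collection rule, and does not say that the earlier date governs. And SAP 5 presents itself as listing major changes, so an omission there is a lesser fault.

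Much of this stands. A reader might infer that next-line toxicity will be counted in general; the documents support only that it could be, where recorded. A reader might also infer that it cannot be separated afterwards. That is not so: protocol 11.4.1 records start and end dates and suspected relationship for each event, and subsequent therapies are collected (protocol 7.1.1.4) and summarised (SAP 3.5). The related-event tables are largely protected by investigator causality.

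What does not stand is that the difference is therefore harmless. Section 11.4.2 governs reporting and has no stop, even where it gives causality instructions for serious events between 30 and 90 days after both drugs end. If the 10.7.1 clause is only a collection rule, it contradicts 11.4.2. If it is an analysis limit, the SAP has dropped it without saying so. Either reading needs a correction.

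**Conclusion.** The point holds as an undeclared difference between SAP 4.2 and protocol 10.7.1, made consequential by the protocol's inconsistency on recording. Followed as written, the SAP would count any recorded event that begins on the next line inside the window. The exposed period is up to 90 − *s* days when both drugs stop together, and at most 30 − *s* days when MEDI4736 ended 60 or more days before ibrutinib. The all-causality summaries are the ones affected.

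The size of the effect on rates cannot be derived. It is tempting to multiply an assumed share starting new therapy within 90 days (say 30% to 60%) by an assumed Grade 3 or worse rate on it (20% to 50%), giving 0.30 × 0.20 = 6 to 0.60 × 0.50 = 30 percentage points. Neither input has a source in the documents; SAP 5 reports discontinuations for progression, not when or whether new therapy began. The product also assumes that every such event was recorded and that none of these subjects had an earlier Grade 3 or worse event. Tables count subjects with at least one occurrence, so those who had one would add nothing.

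Nor should the Phase 1b primary objective be read as putting the dose decision at risk. Dose-limiting toxicity is assessed from Cycle 1 Day 1 to Cycle 2 Day 1, which this window cannot reach. Safety analyses are descriptive, and no error rate or efficacy conclusion changes.

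**What to change.** In SAP 4.2, end the item 1 window at the earlier of (a) the 30/90-day date already defined and (b) the start of new anticancer therapy. Keep item 3, so that study-drug-related events count whenever they start. If the sponsor prefers the longer window, SAP 5 should declare the change with a reason, and a table cut at new therapy should be added.

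Reconcile protocol 7.1.1.5, 10.7.1, 11.4.2 and Appendix 1 so that sites have one rule on recording events after new therapy, and reword the 10.7.1 clause to say which date governs.

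The cost is one SAP sentence and a protocol alignment. No new data are needed: subsequent therapies are already collected, and 10.7.1 itself relies on their start date. The downside is that late events after new therapy that the investigator does not attribute to study drug leave the main tables. A separate listing would keep them visible.
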